5.63 Reaction Management & Protections against Risk

All research staff will receive training in human subjects research via the online Collaborative Institutional Training Initiative (CITI) and will undergo research credentialing procedures at University Cleveland Medical Center. In keeping with good clinical practice policy (NOT-OD-16-148), we will ensure that all key personnel and staff receive approved training in Good Clinical Practice Training. Documentation of successful completion of the training will be kept in our NIH Regulatory Binder.

The consent form will specifically address the risk that the surveys may evoke emotions. Subjects will be told the range of topics addressed in the surveys and will be informed that they can skip a question if they wish and/or stop the interview at any time. If during the data collection interview a subject becomes distressed, we will provide a referral (with the subject's permission) to the social worker for further assessment and support. The nurse interventionists will assess distress for the caregiver subject group and explore the nature of their distress. They will make a professional assessment as to whether the caregiver needs a professional referral. We are assessing caregiver depression and anxiety using the PROMIS measures. Since these two constructs are highly correlated, we will use the depression screening as a tool to determine whether the caregiver subject needs a referral. A score of 1.5 standard deviations above the general population will be considered the threshold to make a referral to the oncology social worker. The research assistant will be collecting these data and there is a calculated field in REDCap that will notify the research assistant if the caregiver subject has scored above the threshold.

For the duration of the COVID-19 pandemic, in-person contact with research staff will be limited to one session with the nurse interventionist for caregivers randomized to the intervention group. Nurses will follow UH and CWRU policies regarding symptom screening and masking for both the nurse interventionist and the caregiver. All equipment used in the intervention will be sanitized thoroughly before and after use. Intervention caregivers who screen positive for COVID-19 symptoms will not be eligible to participate in the study. They will be informed of their ineligible status and told to contact their PCP regarding testing and treatment. If a nurse interventionist screens positive, they will not meet with any subjects and will follow CWRU policies regarding return to work. Another interventionist will meet with the caregiver instead. If the interventionist tests positive for COVID-19, CWRU Employee Health and the UH IRB will be notified immediately and we will follow their guidance to make sure that research subjects who met with that interventionist recently are notified and given appropriate guidance.

As part of protection of human subjects, data will be protected as well. Access to the database will be limited to the project team. Data and the study log, linking subjects' identifiers with their code number, will be stored on REDCap. The de-identified data from REDCap will be downloaded to a password-protected encrypted drive that will be kept in a locked office in the School of Nursing, as described above, when ready for data analysis. The separate passwords for the data files will only be known to the PI, project manager, research assistants, and nurse interventionists. Consent forms, the only paper form containing names, and any paper data forms will be kept separately in locked file drawers, in a locked study office in the School of Nursing. Data sharing with other investigators will occur once human subject identifiers have been removed from the data set and a data-sharing agreement has been obtained.

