3.0 RESEARCH SUBJECT SELECTION AND ELIGIBILITY

Setting

Radiation Therapy Departments of the Seidman Cancer Center at the University Hospitals main campus, satellite community facilities, and MetroHealth Cancer Center.

Population

The sample will consist of family CGs of individuals with HNC, NSCLC, rectal, anal, and esophageal cancer. In this study, a family CG is defined as an adult who is providing daily assistance and/or emotional support to the individual with cancer as identified by the patient. The sample will be drawn from the population of patients at the Cancer Center. Data obtained from the Cancer Center tumor registry show that 403 adult patients with new diagnoses of HNC, rectal, anal, and esophageal cancer (all stages) and stage III NSCLC cancer were evaluated in 2017. Demographic characteristics were: 62.5% male, 37.5% female, 82.4% White, 16.4% Black, and a mean age of 64 years. Fifty-seven percent underwent radiation therapy.

The extension period will include family CGs and patients recruited from MetroHealth, an academic medical center and Cuyahoga County's safety-net health system. It is located in the City of Cleveland, which is racially and ethnically diverse (49% Black, 40% White, 11.9% Hispanic).

Sampling Procedure and Group Assignment

A convenience sample of family CGs will be used.

Inclusion criteria for patients are: (1) 18 years of age or older. (2) Diagnosis of stage I, II, III

cancers of the rectum and anus, stage I, II, III, IVa esophagus; stage II-III NSCLC (excluding those receiving SBRT due to short treatment course); and stage I – IV A/B head/neck (tongue, gum, oral cavity, nasopharynx, oropharynx, hypopharynx, parotid, or larynx). Stage IV A/B will be allowed for HNC and stage IVa for esophagus as the intent of therapy is curative. (3) Has an identified family CG who is willing to participate.

Inclusion criteria for CGs are: (1) 18 years of age or older; (2) family member or friend of an adult patient described above; and (3) identified by the patient as his/her primary CG, who is providing daily assistance and/or emotional support.

Exclusion criteria are: Patients who do not have a caregiver will be excluded. CGs of patients who are receiving hospice care will be excluded because of the patient's poor prognosis and multiple issues associated with end-of-life care. CGs who are themselves undergoing active cancer treatment will be excluded (hormonal treatment allowed).

Projected Enrollment

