For the duration of the COVID-19 pandemic, patient and caregiver consent will be obtained remotely by phone or electronically through Redcap whenever possible. If remote consent is not feasible due to the timing of treatment, patient or caregiver factors, or enrollment issues, we will return to our previous in-person consenting protocol, following all hospital guidelines regarding masking and distancing. The remote consenting protocol is as follows: at the new patient visit (NPV) or CT Simulation visit the radiation oncology staff, such as the Nurse Partner, will give the patient our IRB-approved study brochure and two (2) paper copies of the patient and caregiver consent forms. If the NPV is completed via telehealth or there are insufficient clinical notes to assess eligibility, the brochure and consent form will be given to the patient at the in-person CT simulation visit. The brochure contains opt-out information for patients who do not wish to be contacted about the study. Instructions are to call the study office telephone number to opt out of the study. This opt-out is a short time frame of 2 days, and will be pointed out to the patient by the medical staff. If no call or email from the patient is received within 2 days, the study team will call the patient and discuss the research using a script (attached). If the patient gives verbal consent to participate and identifies a caregiver, and the caregiver lives with the patient and is available, we will offer to speak with them together on the phone to answer any questions about the consent.

Secure REDCap links to the patient and caregiver consent forms will be sent to their preferred email addresses. The informed consent process will continue on the telephone and, after questions are answered, the patient and caregiver will electronically sign and date the REDCap consent forms. The consenter will also electronically sign and date the REDCap consent form. The enrollment procedure proceeds with contact information being completed via telephone.

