If the patient and/or caregiver do NOT have email or internet access, informed consent will proceed via telephone with the patient and/or caregiver signing paper copies of the consent forms, previously provided by the medical staff. The patient and caregiver will mail the signed forms back to the researcher's office via a study-provided postage-paid envelope (also given at their health care provider visit) and will keep the unsigned copies. The enrollment procedure proceeds with contact information being completed via telephone.

Subjects' capacity to consent will be evaluated by the RA in conjunction with the clinical team. Participants must be cognitively intact, as evidenced by orientation to person, place, and time. They must be able to speak, read, and comprehend English.

All participants are volunteers and non-participation and withdrawal from the study are alternatives to study participation. Patients and caregivers will be told that they may withdraw from the study at any time. There are no risks to non-participation or withdrawal from the study. The RA will explain that participation or non-participation will have no effect on the care that the patient and caregiver will receive from the healthcare team.

For the extension period, caregivers will be offered an additional qualitative interview after completing the intervention. The consent form will give caregivers a choice to opt in and agree to be contacted for an interview. Caregivers randomized to the intervention will be selected for interviews using purposive sampling to select participants with a low score in at least one domain of the social determinants of health. Interviews will be done with 15 caregivers who opted in during the consent process. The interviews will take place after they have completed the intervention.

Once consent is obtained, baseline measures will be collected. All participants will be screened for health literacy using a 4-item Brief Health Literacy Screening Tool (BRIEF), a self-report tool that assesses comprehension to written and verbal health information as well as confidence in filling out medical forms. The research team will employ communication and teaching strategies from AHRQ's Health Literacy Universal Precautions Toolkit⁹⁴ for individuals identified as having limited health literacy.

Once baseline data have been obtained, the Project Director will randomly assign the CG to one of

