5.3 Description of Intervention

The intervention was designed over a one-year period in collaboration with a small team of oncology clinicians. Our focus was to design an intervention that would address the specific, complex challenges of family CGs, while maintaining feasibility for implementation into a busy clinic schedule. The intervention is delivered by an experienced oncology nurse, trained in intervention components, during the patient's course of radiation treatments. It consists of three in-person sessions between the CG and intervention nurse (interventionist) and one follow-up telephone contact after treatment is completed (Table 3). The intervention design was validated by:

- Review of CG intervention literature (primary and meta-analytic research)
- Use of an explicit conceptual framework
- Expert opinion from oncology clinicians
- Our prior descriptive studies
- Qualitative interviews with participants in the pilot study regarding satisfaction and acceptability

Decisions regarding timing and duration of the intervention were based on clinical experience and our longitudinal, descriptive study of patients with HNC, which clearly illustrated the pattern of increasing intensity of side effects through the weeks of radiation treatment and one-month posttreatment. In addition, a systematic review of cancer CG interventions found that problem-solving and skill-building interventions were effective in increasing CG confidence if the interventions were structured, of brief duration, and targeted to specific caregiving needs along the care trajectory.⁹¹ Therefore, based on our clinical experience and these findings, we designed three CG sessions and one telephone follow-up to coincide with the typical patient's experience. **Each session lasts approximately 30 minutes.** The nurse interventionist will record the amount of time required for preparation and delivery of each session. For the duration of the COVID-19 pandemic, sessions 2 and 3 will be delivered by phone rather than in-person. The first session will remain in-person in the radiation oncology clinic or the CWRU School of Nursing if caregivers are not allowed in the hospital. All simulation requiring the mannequins will be completed at that first in-person session. We will also offer an in-person option for sessions 2 and 3 if the caregiver requests additional skills training with the manikins.

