6.0 STATISTICAL ANALYSIS

6.1 Primary and secondary endpoints.

The primary endpoint is difference in caregiver anxiety between the intervention and control groups at 20

weeks post-radiation treatment. Secondary endpoints are caregiver anxiety at the end of radiation treatment and 4 weeks post treatment; caregiver depression, HRQOL, and fatigue at the end of treatment and 4 weeks post-treatment; and patient HRQOL at the end of treatment and 4 weeks post-treatment.

6.2, 6.7, 6.8 Statistical Design, Power, Analysis plan, & Missing data.

An intent-to-treat analysis is planned. Before carrying out inferential statistical procedures, exploratory data analysis will be performed: all variable distributions will be examined and descriptive summary statistics will be provided: including means, standard deviations, and ranges for continuous variables, as well as percentages and frequencies for categorical variables, will be provided to describe the study sample. Variable transformations will be made in cases where distributions are skewed, or otherwise fail to meet the assumptions for analyses; nonparametric procedures will be used where transformations would be inappropriate. Plots will be used to describe the data and identify outliers and influential observations.

Aim 1

Analysis. The primary analysis for Aim 1 will be to compare the control and CG intervention arms with respect to CG anxiety at T4 (20 weeks postradiation treatment). A linear mixed model repeated measures analysis will be used to obtain mean changes from baseline in anxiety scores at Times T2, T3, and T4, using baseline anxiety as a covariate, also adjusting for covariates described in Table 4. A contrast of means will be constructed to compare arms with respect to change in anxiety at T4 (primary analysis) at the 0.05 significance level. In addition, the baseline characteristics of the two treatment groups will be compared using appropriate 2-sample tests for continuous or binary outcomes, and in a secondary analysis, characteristics found to differ between groups at baseline will be adjusted for in the linear mixed model. A secondary analysis will test for differences between groups at the other postbaseline time points, using the Tukey method to control the familywise error rate on a per outcome basis. Other CG outcomes will be compared between groups using a similar approach.

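### The COVID-19 symptom rule, read literally, ends study participation for intervention caregivers after randomisation, and it is not reconciled with the intent-to-treat plan

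*Combined protocol and SAP*

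**What the plan says.** **Order of events.** Section 4.0 places consent and baseline measures before allocation: "Once baseline data have been obtained, the Project Director will randomly assign the CG to one of" two groups. Session 1 of the intervention comes after that. Under the pandemic arrangements in section 5.3, "The first session will remain in-person in the radiation oncology clinic", with the School of Nursing as the alternative venue. Sessions 2 and 3 move to the telephone, although "We will also offer an in-person option for sessions 2 and 3 if the caregiver requests additional skills training with the manikins".

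**The rule.** Section 5.63, in a paragraph on pandemic precautions, says "Intervention caregivers who screen positive for COVID-19 symptoms will not be eligible to participate in the study" and continues: "They will be informed of their ineligible status and told to contact their PCP regarding testing and treatment". It gives no rescreening, deferral or follow-up provision.

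**Eligibility.** The exclusion criteria in section 3.0 contain no COVID-19 item. The only one that concerns the caregiver's own health is "CGs who are themselves undergoing active cancer treatment will be excluded", with hormonal treatment allowed.

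**Analysis.** Section 6.0 states: "An intent-to-treat analysis is planned". The Aim 1 model takes changes in anxiety at T2, T3 and T4 with baseline as a covariate. The multiple imputation described in the closing summary is for missing predictor values. Section 6.6, on un-evaluable and ineligible participants, reads N/A.

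**Data collection.** Section 5.4 allows measures in both arms to be collected by mail, emailed survey or telephone as well as in person. Section 5.2 records the number of sessions received as intervention dose.

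**The concern.** A caregiver becomes an intervention caregiver only by being randomised, so this cannot be a pre-enrolment screen. A rule that then declares that person ineligible for the study, with no counterpart for controls, is a post-randomisation removal in one arm. If site staff followed it literally, T2-T4 measures could stop being sought from those caregivers. Intent-to-treat analysis fixes the arm in which people are counted, but it cannot supply outcomes that nobody collected. The safety committee's monitoring of differential attrition (section 5.61) would reveal an imbalance but has no analysis rule attached. At stake is the comparability of the arms on the primary endpoint, caregiver anxiety at T4.

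**Working it through.** **1. The passages side by side.**

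| Question | Where | What the text gives |
|---|---|---|
| When does the rule act? | 4.0, 5.3, 5.63 | After baseline and randomisation, around an in-person session |
| Whom does it name? | 5.63 | Intervention caregivers only |
| What is lost? | 5.63 | Eligibility for the study; the session is not named |
| Is it an exclusion criterion? | 3.0 | No |
| What happens to follow-up? | 5.63, 5.4 | 5.63 is silent; 5.4 provides measures for both arms, without a COVID-19 exception |
| Who is analysed? | 6.0, 6.6 | Intent-to-treat, not defined further; N/A for ineligible participants |

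Two readings are open. On the session-only reading, 5.63 is badly worded but 6.0 and 6.6 stand. On the literal reading, 5.63 creates a class of randomised but ineligible caregivers, and 6.0 and 6.6 do not deal with it.

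**2. Effect on the primary model.** The outcomes are changes at T2, T3 and T4. A caregiver removed before T2 has a baseline value and no outcome row, so contributes nothing to the T4 contrast. Imputing predictors does not alter that. This would be true of any dropout before T2; what is particular here is that the cause is a rule written for one arm.

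**3. The plan's own figure, used as a yardstick.** Section 6.0 gives a detectable difference of 0.36 SD at 80% power with 81 per arm, a baseline-T4 correlation of 0.50 and two-sided 0.05. The standard error is sqrt((2/n)(1 - 0.50²)), which is 0.136 at n = 81. Power at 0.36 SD is then Φ(0.36/0.136 - 1.96) = 75%, not 80%; with 90 per arm (180 before dropout) it is 79.6%. That is a separate matter, and 0.36 SD serves below only as a scale.

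**4. Possible size.** The documents supply none of the three inputs, so all are assumptions:

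- p, the share of the intervention arm enrolled under the rule: 25-100% (the amendment log dates the screening entry to 5/28/20; no end date is given);
- f, the share of those removed: 2-10%;
- d, the difference in T4 anxiety between those removed and those who remain, in either direction: 0.3-0.8 SD.

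Losing the removed caregivers shifts the arm mean by p × f × d. Caregivers removed = 122 × p × f, taking 122 per arm as 244/2. Type I error is Φ(-1.96 + shift/SE) + Φ(-1.96 - shift/SE), with SE 0.136 at 81 per arm and 0.118 at 107 per arm (214/2, equal arms assumed).

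| Case | p × f × d | Shift (SD) | Share of 0.36 | Removed of 122 | Type I error, 81 / 107 per arm |
|---|---|---|---|---|---|
| Low | 0.25 × 0.02 × 0.3 | 0.0015 | 0.4% | 0.6 | 0.050 / 0.050 |
| Central | 0.50 × 0.05 × 0.5 | 0.0125 | 3.5% | 3.1 | 0.051 / 0.051 |
| Whole arm under rule | 1.0 × 0.05 × 0.5 | 0.025 | 6.9% | 6.1 | 0.054 / 0.055 |
| All inputs at maximum | 1.0 × 0.10 × 0.8 | 0.080 | 22% | 12.2 | 0.090 / 0.104 |

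If the difference is equally present at baseline, adjustment with r = 0.50 leaves half of each shift, at most 0.040 SD. The last row needs all three assumptions at their limit together and is not a plausible estimate.

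**The case against.** The best defence is that the sentence was meant only to cancel the face-to-face session. The paragraph opens by limiting in-person contact and goes on to masking and equipment cleaning; the matching rule for a nurse is about not meeting subjects; section 3.0 has no COVID-19 criterion; and the log entries of 5/28/20 list no change to sections 3.0 or 6.0. This is a fair reading and may be what was intended. But the text names the study and tells caregivers they are ineligible, so it does not settle the matter.

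Three stronger readings are tempting and are not supported:

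- A reader might infer that T2-T4 data from these caregivers are lost or dropped. Nothing says so, and section 5.4 provides measures for both arms. This is an unresolved conflict, not a demonstrated breach of intent-to-treat.
- A reader might take the N/A in 6.6 as an error in its own right. It can equally mean that no allowance is needed because everyone randomised is analysed. It is wrong only if 5.63 is read literally.
- A reader might see unequal treatment in the other in-person contacts. Consent in person, where "we will return to our previous in-person consenting protocol", precedes randomisation, and the optional in-person sessions 2 and 3 exist only in the intervention arm. During the pandemic, controls have no scheduled research session to screen for, which explains the one-sided wording. It does not undo its effect if the rule is applied literally.

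It is also fair to say that the likely number affected sits well inside the planned dropout of 10% (parent study) or 12% (with the extension).

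**Conclusion.** The point holds as an unreconciled conflict of wording, at minor severity. Section 5.63 as written ends study eligibility for some randomised intervention caregivers, and the intent-to-treat statement does not say how they are handled. Whether any bias follows depends on three things the documents do not give: how staff applied the rule, how many screened positive, and how their anxiety compared with that of the others. Direction is therefore unknown. Size is probably small, with a shift of about 0.0125 SD and a type I error of about 0.051 in the assumed central case. The documents do not show that the trial result is biased or that the analysis breaks intent-to-treat.

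**What to change.** Reconcile 5.63 with 6.0 and 6.6 in a short clarification:

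- A positive screen does not remove a randomised caregiver from the study cohort.
- T2, T3 and T4 measures are still sought by the mail, emailed-survey or telephone routes in section 5.4.
- The caregiver is analysed in the randomised arm, and sessions received are recorded as dose under section 5.2.
- Section 6.6 says this in place of N/A.
- The report gives, by arm, the number already removed under the rule, and includes their existing data in the intent-to-treat analysis as far as consent allows.

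How in-person contact is handled after a positive screen is for the study team to decide.

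The cost is low: a few sentences and one count, because remote collection and dose recording are already in the protocol. If enrolment under the rule has ended, only the analysis statement, the count and the use of existing data remain to be done.
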